3.2 Intervention phase procedures

3.2.1 Randomization

For this trial, the unit of randomization will be the individual participant. Participants will enroll and complete a baseline survey before being randomized to a study arm, a qualitative interview and/or audio-recording of their visit by research staff with the use of a REDCap randomization instrument, based on an allocation table. Results of randomization will be documented in REDCap.

Individuals will not be considered participants until they are randomized. Prior to being randomized, if an eligible patient participant does not wish to continue with study procedures, they will be considered as a “decline to participate.” If they do not wish to continue with study procedures after the point of randomization, they will be considered “dis-enrolled” (see dis-enrollment procedures).

Intervention arm randomization

Randomization (#1) to the study’s intervention (HIV prevention DST) or control arms will occur immediately before receipt of the intervention.

In-depth interview and audio-recording randomization

After enrollment in the study and randomization to the DST or control arms, participants will then be randomized to determine if they will be invited to conduct a qualitative interview or audio-recording of their counseling visit. This randomization will be based on participant’s response during the eligibility screening regarding racial/ethnic identity.

For participants who self-identify as Black or Latina, or multiracial including Black or Latina, a random number generator will be used within each study arm (those randomized to the DST or control) to determine if the participant will be invited to complete an in-depth qualitative interview after their visit or have their counseling session audio-recorded. If yes, the participant will be offered the opportunity to complete an interview or audio recording and consented if they agree.

Participants who do not identify as Black or Latina, or multiracial, will only be randomized to have their counseling session audio-recorded or not. If yes, participants will be invited to participate and consented if they agree.

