### 1.2 Study Design and Randomization

The study is a parallel-group Randomized Control Trial with up to 384 participants recruited from family planning sites in Duval County, Florida and randomized 1:1 into two groups (192 in intervention group, 192 in control). Study duration: 3 months.

Treatment: Participants in this arm will receive the HIV prevention DST intervention and will receive the intervention immediately before their provider visit.

Control: Participants in this arm will receive usual care.

Randomization procedures: Randomization will be implemented using randomly permuted blocks of randomly selected size 2 and 4, stratified by clinic and race. All randomization will occur by research staff with the use of a REDCap randomization instrument.

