##### 2.1.2.2 Secondary variables

- **Number of Patients Reporting PrEP use:** Participants will be contacted at follow-up and asked if took PrEP in the past 3 months regardless of where it was obtained.

- **Patient-Perceived HIV risk:** Participants will be asked about how worried they are about getting HIV in the next 6 months.
- **Knowledge of PrEP:** Participants will be asked a series of questions about PrEP to assess PrEP knowledge.
- **Decisional Conflict:** Participants will be asked questions derived from the Decisional Conflict Scale to provide a measure of decision quality about their HIV prevention decision immediately following their visit.
- **Interpersonal Quality of HIV Prevention Care:** A scale for patient-centered HIV prevention counseling focusing on patient preferences and reflecting satisfaction and confidence in the counseling session, derived from the Interpersonal Quality of Family Planning Care Scale developed by the PI.
- **Intention to Use Any HIV Prevention Method:** Participants will be asked if they plan to use any HIV prevention method after the initial visit.
- **Satisfaction with Information Received about HIV Prevention:** Participants will be asked about their satisfaction with HIV prevention counseling.
- Confidence in decision to use an HIV prevention method. A one-time, one-item measure of certainty of plan to use HIV prevention after the initial visit. Participants can select from 4 options: 1 ("completely unsure"), 2 ("mostly unsure"), 3 ("mostly sure, but not 100%"), or 4 ("100% sure").
- **Perceived Quality of Information Received about HIV Prevention:** Participants will also be asked questions about the perceived quality of the HIV prevention information they received during their health care visit.
- **Acceptability of HIV Prevention Methods:** Participants will be asked to rate their preference for a method (even if they never used it). Participants can select from condoms, PrEP, PEP, treatment as prevention, regular partner testing, or other method.
- **Acceptability of the Decision Support Tool:** Participants in the experimental arm are asked four questions about their experiences using the DST.
- Perception of the Decision Support Tool: Participants in the experimental arm will be asked about the degree to which they liked/disliked the tool. Response options vary: "I did not like it at all", "I somewhat disliked it", "I somewhat liked it", "I really liked it".

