## 2.2 Hypotheses

1. The intervention will result in significantly higher number of PrEP prescriptions compared to the control group.
2. The intervention will result in significantly higher number of individuals reporting PrEP initiation compared to the control group.
3. The intervention will result in significantly higher level of patient-perceived HIV risk post-visit compared to the control group.
4. The intervention group will report significantly higher PrEP knowledge compared to the control group.
5. The intervention group will report significantly higher quality of HIV care compared to the control group.
6. The intervention group will report significantly higher intention to initiate any HIV prevention method compared to the control group.
7. The intervention group will report significantly higher satisfaction with information received about HIV prevention compared to the control group.
8. The intervention group will report significantly higher confidence in decision to use an HIV prevention method compared to the control group.
9. The intervention group will report significantly higher acceptability of HIV prevention methods compared to the control group.
10. The intervention group will report significantly lower decisional conflict, as documented by the full scale and subscales, compared to the control group.
11. The intervention will result in significantly higher number of individuals reporting ongoing PrEP use at 3 months post-visit compared to the control group.
12. A significantly higher proportion of the intervention group will report use of any HIV prevention method at 3 months-post study initiation compared to the control group.
13. A significantly higher proportion of the intervention group will report significantly higher continuation of any HIV prevention method at 3 months-post study initiation compared to the control group.
14. The intervention group will report high acceptability of the DST.
15. A high proportion of the intervention group will report positive impression of the DST.
16. A high proportion of the intervention group will report willingness to use the DST at a future visit.
17. A high proportion of the intervention group will report willingness to recommend to a friend.
18. The intervention group will report high satisfaction with the DST.

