## 1. STATISTICAL METHODOLOGY

### 3.1 General methodology

All outcomes will be presented using descriptive statistics; normally distributed data by the mean and standard deviation (SD) and skewed distributions by the median and interquartile range (IQR). Demography and baseline characteristics will be statistically summarized by treatment group. For binary or categorical items, counts and proportions will be calculated and reported. For continuous outcomes, we will use t-tests for independent samples and for categorical outcome we will employ  $\chi^2$  or Fisher's exact-tests to examine baseline differences between training and control group in demographic data or measured variables. Categorical variables will be assessed and collapsed in cases of small cell sizes for increased power. Scale items of questionnaires (e.g., Decisional Conflict Scale) will be recoded (where applicable) and a scale mean or sum score will be calculated and reported. Composite scale variables will be assessed for skewness through histograms and normal Q-Q plots. Where the normality assumption is not met, median and IQR will be reported. Sign tests will be used to detect differences between groups. Further, in instances where a strong skew is detected, scales will be transformed into binary variables and analyzed as binary data.

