#### 3.3.2 Secondary data analyses

The analysis plan for H2-H9 is as follows:

Summary statistics will be presented by treatment group. Differences between study groups at  $t_1$  will be assessed through  $\chi^2$  or Fisher's exact tests as appropriate. Cohen's d will be calculated as measure for effect size.

The analysis plan for H10 is as follows:

Full scale and subscales will be scored as instructed in the [Decisional Conflict Scale](#) manual. Summary statistics will be presented by treatment group for the full scale and by subscale. To assess differences in scale score distribution between groups, we will perform t-tests or sign tests as appropriate. In case of high positive skew (as common in the literature) we will create binary variables demarcating no conflict versus any conflict and perform  $\chi^2$  tests. Cohen's d will be calculated as measure for effect size.

The analysis plan for H11-H13 is as follows:

Summary statistics will be presented by treatment group. Differences between study groups at  $t_2$  will be assessed through  $\chi^2$  or Fisher's exact tests as appropriate. Cohen's d will be calculated as measure for effect size.

The analysis plan for H14-H18 is as follows:

Summary statistics will be presented for the intervention group.

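### The SAP names sign tests to compare non-normal scale scores between two independent arms; a two-sample test such as the Wilcoxon rank-sum is needed

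*SAP*

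**What the plan says.** SAP 3.1 has composite scales checked for skewness with histograms and normal Q-Q plots. It then gives two linked rules: "Where the normality assumption is not met, median and IQR will be reported", followed by "Sign tests will be used to detect differences between groups". Strongly skewed scales are instead made binary.

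The H10 paragraph of SAP 3.3.2 applies the same scheme to the Decisional Conflict Scale and its subscales: "we will perform t-tests or sign tests as appropriate". It adds an exit to a chi-square test of any versus no conflict: "In case of high positive skew (as common in the literature) we will create binary variables".

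The contrast is between arms. H10 in SAP 2.2 expects "lower decisional conflict, as documented by the full scale and subscales, compared to the control group".

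On the design, SAP 1.2 says "The study is a parallel-group Randomized Control Trial with up to 384 participants", allocated 1:1 with 192 per arm. Protocol 3.2.1 says "the unit of randomization will be the individual participant". SAP 2.1.2.2 describes decisional conflict as "a measure of decision quality about their HIV prevention decision immediately following their visit".

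**The concern.** A sign test counts positive and negative differences, either within matched pairs or from a value fixed in advance. Neither document describes matched women, a baseline decisional conflict score or a reference value, so the named test has no unique definition for this comparison. The t-test offered beside it can be carried out on two independent arms; the sign test cannot.

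An analyst could force the test onto the data by pairing unrelated women or by treating the other arm's median as known. Otherwise a different test must be substituted, and that choice would be made with the data in view, which a prespecified plan should prevent. Decisional certainty is Aim 1c in SAP 1.1 and is listed among the main outcomes in the SAP overview. The rule is also applied several times, to the full scale and to each subscale.

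**Working it through.** **Inputs.** From the documents: 192 per arm (SAP 1.2); two-sided alpha 0.05 and an evaluable total of 320, or 160 per arm (SAP 1.5). The documents give no effect size, distribution or power for any scale outcome. The 0.3 SD effect and the distribution shapes below are therefore assumptions.

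**The plan's own figure.** The standard two-proportion formula with continuity correction, for 5% versus 15% at 80% power, gives 160 per arm, or 320. This reproduces SAP 1.5. It rests on the binary primary outcome and does not depend on the test chosen for H10.

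**Option (a): pair women across arms arbitrarily.** For normal scores 0.3 SD apart, the chance that a woman in one arm scores above a woman in the other is Φ(0.3/√2) = Φ(0.212) = 0.584. With 192 pairs, the exact two-sided sign test rejects at 81 or fewer, or 111 or more, positive signs.
- Size under Binomial(192, 0.5): 3.6%.
- Power under Binomial(192, 0.584): 59.6%.
- Rank-sum approximation: 0.3 × √(192/2) × √(3/π) = 2.87, so power is Φ(2.87 − 1.96) = 82%.

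**Option (b): treat the other arm's observed median as fixed.** That median has sampling error of its own. With equal arms, this doubles the variance of the sign count, but the test allows for only half of it. The large-sample type I error is 2 × [1 − Φ(1.96/√2)] = 2 × [1 − Φ(1.386)] = 16.6%, before the discreteness of the count lowers it slightly.

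**Simulation** (10,000 runs per setting, assumed 0.3 SD effect). Power:

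| Assumed shape | Per arm | Rank-sum | Sign, arbitrary pairs | Two-sample median test |
|---|---|---|---|---|
| Normal | 192 | 81.4% | 59.4% | 65.3% |
| Gamma, skewness 1 | 192 | 88.6% | 68.4% | 70.4% |
| 0-100 score, 65 values, means 30 and 23.85 | 192 | 87.9% | 72.3% | 70.7% |
| Normal | 154 | 72.2% | 52.8% | 55.6% |
| Gamma, skewness 1 | 154 | 80.9% | 61.2% | 61.2% |
| 0-100 score, as above | 154 | 80.5% | 61.2% | 61.7% |

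The 154 per arm is 192 × 0.8 = 153.6, rounded up; it is an assumed loss.

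Type I error over the six matching null settings:
- Rank-sum: 4.5-5.1%.
- Sign test on arbitrary pairs: 3.5-4.5%.
- Sign test against the other arm's observed median: 13.3-15.6%.

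**Dependence on the pairing.** In 60 gamma datasets with rank-sum p between 0.005 and 0.015, each was re-paired 1,000 times. The central 95% range of the sign-test p ran, at the median, from 0.001 to 0.35, and 54% of pairings fell below 0.05. In a separate run of 2,000 trials per setting (normal and log-normal shapes, 160 and 192 per arm), two random pairings of the same data disagreed on significance in 26-27% of trials when there was an effect.

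**The case against.** The strongest reply is that nobody would pair unrelated women or treat a sample median as known. On this view the authors meant a rank-sum or two-sample median test, the latter fitting the median and IQR reporting, and the simulations only show hypothetical misuse. It is fair that the SAP proposes neither workaround, so those figures show what a literal reading would cost, not what will happen. But the wording occurs twice and does not say which two-sample test is meant. The candidates also differ: at 192 per arm the median test has 65-71% power, against 81-89% for rank-sum.

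The affected branch is narrow. Near-normal scores go to a t-test, and the SAP itself expects high skew, which goes to chi-square. That limit stands. However, the SAP sets no cut-off between failing normality and being strongly skewed, and each subscale is judged separately, so the middle branch can be reached.

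Two points about the figures are right. Normal scores would not enter this branch; without that shape, the gap at 192 per arm is 16-20 points (87.9 − 72.3 = 15.6; 88.6 − 68.4 = 20.2). The plan's 20% allowance concerns 3-month follow-up, whereas decisional conflict is collected after the visit, and no loss rate is given for that survey. The 154-per-arm rows are therefore only a sensitivity case.

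On scope, SAP 3.1 words its rule for composite scales generally, so it might be read to reach the interpersonal-quality scale (H5). SAP 3.3.2 specifically assigns chi-square or Fisher tests to H2-H9, and that reading is used here.

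**Conclusion.** The concern holds. The SAP twice prescribes a one-sample or paired test for a comparison of two independent groups and names no valid two-sample non-parametric alternative. That conclusion follows from the design and needs no assumption.

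The size of the effect does rest on assumptions. With a 0.3 SD effect and the two non-normal shapes at 192 per arm, arbitrary pairing costs about 16-20 points of power relative to rank-sum. Using the other arm's median as fixed roughly triples the false-positive rate.

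The reach is limited to H10, for scores that are non-normal but not dichotomised. The primary analysis (H1), H2-H9 and H11-H13 are assigned chi-square or Fisher tests, and the sample size does not change. This should be corrected before the data are analysed, but it does not threaten the trial's main conclusion.

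**What to change.** In SAP 3.1 and in the H10 paragraph of SAP 3.3.2, replace the sign test with the two-sample Wilcoxon rank-sum (Mann-Whitney) test. A two-sample median or permutation test would also be valid. Rank-sum is suggested because it had clearly more power than the median test in every setting examined. The van Elteren version, stratified by clinic and race to match the randomisation in SAP 1.2, is an option. The chi-square comparison of any versus no conflict under high skew can stay as written.

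The cost is a wording change in two places. Rank-sum is one standard Stata command, and no data collection, sample size or study procedure changes.

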### 1.1 Study objectives

Aim 1a: Women who use the HIV prevention decision support tool will be more likely to have initiated PrEP within 3 months compared to women who received standard counseling at the time of their initial appointment.

Aim 1b: The HIV prevention decision support tool will increase women's knowledge of PrEP and other HIV prevention methods compared to women who received standard counseling at the time of their initial appointment.

Aim 1c: The HIV prevention decision support tool will increase participants' decisional certainty in their choice of an HIV prevention method compared to women who received standard counseling at the time of their initial appointment.

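### Decisional conflict (H10): the test is picked after an unquantified look at skew, from a t-test, a sign test that does not fit independent arms, and a no-versus-any split that usually loses power

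*SAP*

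**What the plan says.** SAP 3.1 (General methodology) sets the general rule. "Composite scale variables will be assessed for skewness through histograms and normal Q-Q plots". If normality fails, medians are reported and "Sign tests will be used to detect differences between groups". Beyond that, "in instances where a strong skew is detected, scales will be transformed into binary variables and analyzed as binary data". No skewness value defines the trigger and no general cut-point is given.

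SAP 3.3.2 (Secondary data analyses) applies this to H10, which covers the full Decisional Conflict Scale and its subscales. The default is that "we will perform t-tests or sign tests as appropriate". The fallback reads: "In case of high positive skew (as common in the literature) we will create binary variables demarcating no conflict versus any conflict", followed by a chi-square test. So for this scale the cut-point is named in advance, but the condition for using it is not quantified.

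The analysis bears on Aim 1c in SAP 1.1: "The HIV prevention decision support tool will increase participants' decisional certainty in their choice of an HIV prevention method".

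The two documents differ on blinding. Protocol 3.2.2 has staff blinded to tool use during quantitative analysis. SAP 1.6 says that neither participants nor the study team are blinded.

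**The concern.** There are three linked problems, all within H10.

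1. **The test is not fixed.** Which of three analyses is run depends on how plots of the trial data look to the analyst. The choice could also differ between the full scale and each subscale.
2. **One option does not fit the design.** A sign test compares paired values, or one sample against a fixed value. The arms here are separate women randomized 1:1 (SAP 1.2), so there are no pairs.
3. **The expected option discards information.** Skew does not require a binary split, because a rank test on the full score handles it. Cutting at zero treats a woman with slight conflict and one with severe conflict alike. If the tool reduces the degree of conflict without removing it, this analysis can hardly see the effect.

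At stake are the power and interpretability of a secondary result tied to a stated aim, and a reader's confidence that the reported test was not picked for its result.

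**Working it through.** **The plan's own figure.** The only power statement (protocol 7.2, SAP 1.5) concerns PrEP uptake of 5% vs 15%, two-sided alpha 0.05, 80% power. Uncorrected:

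n = [1.96·√(2·0.10·0.90) + 0.842·√(0.05·0.95 + 0.15·0.85)]² / 0.10² = (0.832 + 0.352)² / 0.01 ≈ 140.1, rounded up to 141 per arm.

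With the continuity correction, n′ = (n/4)·[1 + √(1 + 4/(n·0.10))]² ≈ 160 per arm. The stated 320 therefore reproduces, and 384 = 320 × 1.20. This gives no power for any scale, and the documents give no item count, range, SD or share at zero for decisional conflict. Everything below rests on assumptions.

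**Main check: a shift of the whole score.** Assume a latent normal score with a floor at zero, a 0.3 SD downward shift with the tool, 192 per arm and two-sided 0.05. If a share p_C of controls scores zero, the intervention share is p_I = Φ(Φ⁻¹(p_C) + 0.3). Split power is

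Φ{ [|p_I − p_C| − 1.96·√(2p̄(1−p̄)/n)] / √[(p_C(1−p_C) + p_I(1−p_I))/n] }.

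For p_C = 20%: p_I = Φ(−0.842 + 0.3) = 29.4%. The numerator is 0.094 − 1.96 × 0.0440 = 0.0077, the denominator is 0.0438, and the power is Φ(0.18) = 57%. The other rows follow the same way. The simulated columns put the rank-sum test beside the split.

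| Controls at zero | Intervention at zero | Split, formula | Split, simulated | Rank-sum, simulated |
|---|---|---|---|---|
| 20% | 29.4% | 57% | 58% | 80% |
| 40% | 51.9% | 65% | 64% | 74% |
| 60% | 71.0% | 62% | 62% | 67% |

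At 70% of controls at zero the gap is about 3 points. With 160 per arm the three rows become 73% vs 51%, 67% vs 57% and 59% vs 55% (rank-sum vs split).

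**Other mechanisms (160 per arm, simulated).**
- The tool only lowers the degree of conflict among women who have some (mean × 0.75, 10% at zero in both arms): t-test 75%, rank-sum 55%, split 6%.
- The tool only moves women to zero (30% to 42%): split 61%, rank-sum 46%, t-test 23%. The formula agrees for the split: (0.12 − 1.96·√(2·0.36·0.64/160)) / √((0.21 + 0.2436)/160) = 0.28, and Φ(0.28) = 61%. With 192 per arm, moving women only to zero likewise favours the split (67% vs 53%).

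**Type I error (160 per arm, no true difference, 10% to 70% at zero).**
- Switching from t-test to split when pooled skewness exceeds 1 gave 4.8% to 5.2%. The trigger fired in almost every run, so this alone is a weak test of switching. The reasoning is general, though: under the null, the shape of the pooled scores says nothing about how they divide between arms.
- Taking the best of t-test, rank-sum and split gave about 9% to 11%.
- Adding two further cut-points (the median and 25) gave about 11% to 16%.

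**The case against.** A reader might infer several stronger things that the documents do not support.

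- **That the false-positive rate is inflated.** SAP 3.1 describes a look at distribution shape, not a choice by p-value. Done on pooled scores blind to arm, it keeps the error near 5%. For decisional conflict the cut-point is also fixed in advance. What stands is that the SAP does not require a pooled or blinded look, and the protocol and SAP disagree on whether analysts are blinded. The risk is open rather than shown.
- **That the split always loses power.** It does not. The loss is small when most women score zero and reverses when the tool acts only on the share at zero. The largest gap in the table also belongs to the least skewed case: pooled skewness was only about 0.8 with 20% at zero, which might not count as high skew. What stands is that the split usually loses, and loses badly when few women score zero or when only the degree of conflict changes.
- **That Aim 1c depends on H10 alone.** The one-item confidence measure (H8) also addresses certainty.
- **That the three-way choice governs every scale.** SAP 3.3.2 assigns chi-square or Fisher tests to H2–H9 and H11–H13. The choice between t-test, sign test and split is written for H10 only. The separate rule, "Categorical variables will be assessed and collapsed in cases of small cell sizes for increased power", concerns sparse categories and not skewed scales.

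It can also be said that insisting on a rank test is partly a preference. That is fair as regards power, since no test wins under every mechanism. It does not rescue the sign test or the missing trigger.

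**Conclusion.** The concern holds as a secondary-outcome point that should be corrected. H10 has no single prespecified test, one of its options does not fit two independent arms, and its expected option usually costs power: about 22, 10 and 5 points with 20%, 40% and 60% of controls at zero, under a 0.3 SD latent shift and 192 women per arm with complete data. Those figures depend on an assumed distribution, and the sign of the difference changes if the tool works only by removing conflict entirely. Inflation of the false-positive rate, to about 9% to 16%, is possible only if the test or cut-point is chosen with knowledge of arm or results, and nothing in the documents says it will be. The primary analysis of PrEP prescriptions (SAP 3.3.1) is unaffected.

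**What to change.** In SAP 3.1 and 3.3.2:

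1. Replace the sign test and the skew-triggered split for H10 with one prespecified Wilcoxon rank-sum test on the full-scale and subscale scores, whatever their shape.
2. Report the probability that a woman in the intervention arm scores lower than a control (the Mann-Whitney estimate), or a proportional-odds ratio, with a 95% CI. Do not use the Hodges-Lehmann difference. Under the same model it was exactly zero in roughly 87% to 90% of simulated trials with 40% of controls at zero and in all of them with 60%, so it would report no difference where one exists.
3. Keep no versus any conflict as a prespecified supportive analysis, with a difference in proportions and 95% CI.
4. For any other scale that will be analysed as binary, fix the cut-point before unblinding. Decide any collapsing of categories on pooled data, blind to arm.
5. Reconcile protocol 3.2.2 and SAP 1.6 on analyst blinding.

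The cost is SAP wording, with no new data and no added participants. The rank-sum test gives up some power if the tool acts only by moving women to zero, which the supportive analysis would show. It also gives up some to a comparison of means if only the degree of conflict changes.
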